3.1.1 Dose Escalation

The study will have 3 alternative dosing schedules:

- **(CLOSED)** Schedule A
 - D1/D5 or D1/D5/D12/D19 (dexamethasone prophylaxis)
- **(CLOSED)** Schedule B: Etanercept Substudy (R/R AML)
 - D1/D5 or D1/D5/D12/D19 (etanercept 2 days prior to each cycle).

The etanercept substudy used etanercept 2 days prior to infusion of each cycle D1, and if applicable, 2 days prior to infusion on D12. [REDACTED]

- **Schedule C** (Table 16 through Table 21): FIH, eIV (R/R AML); MRD+ Group (MRD+ AML)
 - D1/D3/D5/D8 or D1/D3/D5/D8/D12/D19 (dexamethasone prophylaxis)

Note:

- The MRD+ group will use Schedule C for all cycle collections and Table 22 for additional whole blood MRD collection, or Table 23, as applicable.

The initial cohort will begin with Schedule A and will receive 2 doses (1 each on D1 and D5). After reviewing the emerging PK, safety and efficacy data, the DLRT may recommend the administration of additional doses on D3 and D8, to comprise a 2-week cycle with doses on D1/D3/D5/D8 (Schedule C).

[figure not shown]
Additionally, if the following conditions are met, the DLRT may recommend the administration of 2 additional doses (D12 and D19):

- the 2-4 dose regimen (D1/D5 and/or D1/D3/D5/D8) is deemed safe and tolerable
- it is determined from the observed AMG 427 exposures that AMG 427 is rapidly cleared and/or distributed (ie, its observed half-life is much shorter than its predicted half-life)
- efficacy (based on clinical data and pharmacodynamic markers eg, clearance of FLT3⁺ blasts in the blood and/or bone marrow) is observed but is not sustained and addition of D12 and D19 doses may improve the duration or depth of response

Once the DLRT recommends additional doses, all subsequent cohorts will be treated with a 4 or 6 dose regimen in each cycle. The additional doses (if applicable), may be at

the same dose as the preceding dose or may be at higher doses (dose step). A dose step is any dose that is higher for a given subject than the subject has previously received. Dose steps may occur at D3, D5, D8, D12, or D19 infusions.

Starting with an initial lower dose may improve tolerability of subsequently administered higher doses due to initial reduction of the bulk of blast cells, thereby improving efficacy. The DLRT will recommend an initial lower dose, which will not be higher than dose which triggered a DLT. For a schematic overview of the different dose step options see [Figure 2](#) below.

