6.2.1.3 Dose-cohort Study Escalation and Stopping Rules, Dose Limiting Toxicities (DLTs)

A DLT will be defined as any of the events described below occurring in a subject during the DLT window. The DLT window will start on D1 (start of the administration of the first dose) and last for 28 days for all cohorts. Any adverse event occurring outside the DLT window that is determined by the investigator to be possibly related to the investigational product, which is seen more frequently or is more severe than expected or is persistent despite appropriate management, can be determined to be a DLT upon unanimous

recommendation by the DLRT after review of the adverse event and all available safety data.

DLT Evaluation

A subject will be DLT-evaluable if the subject has received the doses planned for the respective cohort, and completed the DLT window of 28 days for all cohorts. The DLT window may also be extended to assess events starting within the window in case the DLT definition is time dependent (eg, in case of neutropenia).

A subject is not DLT-evaluable if he/she drops out before completion of the DLT window for reasons other than a DLT; exception: if a subject has received the planned doses in cycle 1 and drops out within 1 week of the completion of the DLT period due to progressive disease, that subject will be considered DLT-evaluable and will not be replaced. All available safety data for subjects who are not DLT evaluable will still be evaluated and considered in DLRM recommendations. A DLT will be defined as any of the events described below occurring in a subject during the DLT window unless clearly attributable to causes other than AMG 427 treatment. The CTCAE version 4.0 (see [Appendix A](#)) will be used to assess toxicities/adverse events with the exception of CRS (see [Table 6](#) for grading criteria of CRS) and **immune-effector associated neurotoxicity syndrome (ICANS)** (see [Table 8](#) for grading criteria of ICANS).

Events to be considered as DLTs and exceptions are listed below:

- Cases of drug-induced liver injury confirmed by Hy's Law criteria
- Any treatment-related death
- Grade 2 or 3 CRS meeting any of the criteria listed below:
 - Grade 2 CRS that does not resolve, with or without intervention, to \leq grade 1 within 7 days will be considered a DLT
 - Grade 3 CRS that does not resolve, with or without intervention, to \leq grade 2 within 5 days, or \leq grade 1 within 7 days, will be considered a DLT

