6.2.1.4 Dosage Adjustments, Delays, Rules for Withholding or Restarting, Permanent Discontinuation

Treatment Interruption

Significant events attributed to the drug or infusion may require treatment interruption.

Note: The definition of treatment interruption may include interruption of infusion or delay of the subsequent dose.

Events leading to treatment interruption may include:

- The subject experiences a grade \geq 3 adverse event related to the infusion/drug
- Technical problem with the syringe/infusion pump/syringe pump
- The investigational product is incorrectly prepared or administered (eg, overdose)

Treatment Interruption and Re-Start in Case of Adverse Events During the Infusion

Treatment must be modified for any clinically relevant (as determined by investigator) adverse events that occur during the infusion and are related to investigational product, as follows:

- grade 2 adverse event: **Prior to next dose, adverse event must resolve to grade 1 or less for at least 24 hours, including isolated lab abnormalities and organ toxicity labs**
- grade 3 adverse event: Interrupt the infusion until the adverse event is grade ≤ 1 **for at least 24 hours prior to the next dose of AMG 427**. Restart at the same dose if interruption is ≤ 72 hours. If interruption is > 72 hours, restart at a lower dose (last safe dose as **recommended** by DLRT or a lower dose). If the adverse event is a DLT, follow Section 6.2.1.3 for management of DLT.
 - **Subjects who experience CRS grade 3 should have next dose delayed until CRS resolves to grade ≤ 1 for at least 24 hours prior to the next dose of AMG 427 (including isolated lab abnormalities and organ toxicity labs, except for liver function tests, which must resolve to grade 2 or less), and should have next dose(s) reduced by one-half or more, if given on scheduled day (please consult with the study medical monitor).**
- grade 4 adverse events during the infusion: Permanently discontinue the investigational product

The Amgen medical monitor has to be consulted prior to a planned re-start.

In case of a dose reduction, re-escalation to the target dose can be considered for the next infusion if treatment at the lower dose has been well tolerated. An intermediate dose level may be administered prior to stepping up to the target dose after consultation with the Amgen medical monitor.

The subject should be hospitalized for at least 72 hours after re-start of the infusion.

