If possible, the number of infusions at the target dose in a cycle should sum up to the planned number of infusions. In this case, the cycle would still be DLT-evaluable.

Permanent Discontinuation

A subject will permanently discontinue treatment with investigational product in the event of:

- dose-limiting or other unmanageable toxicity
 - except subjects who have experienced a DLT at a certain dose level may continue to receive AMG427 at a lower dose, if AMG 427 has shown efficacy in the specified subject, and the subject's adverse events have reduced to grade 2 or lower, and after discussion with the Amgen Medical Monitor.
- grade 4 CRS
- grade 2 or 3 CRS meeting any of the criteria listed below:

- grade 2 or 3 CRS that does not improve to \leq grade 1 within 7 days
- grade 3 CRS that does not improve to \leq grade 2 within 5 days
- grade 3 CRS at the initial run-in dose for a cycle (ie, at the MTD1) (for cohorts with dose step only)
- If a subject experiences 2 separate grade 3 CRS events
- disease progression as defined by revised IWG response criteria ([Appendix E](#))
- withdrawal of subject's consent to treatment
- subject or investigator not compliant with the study protocol
- occurrence or progression of a medical condition, which in the opinion of the investigator, should preclude further participation of the subject in the study
- a treatment interruption of more than 21 days due to an adverse event not clearly related to the underlying disease (except neutropenia)
- occurrence of a CNS-related adverse event considered related to AMG 427 by the investigator and meeting 1 or more of the following criteria:
 - more than 1 seizure
 - a CNS-related adverse event grade 4
 - a CNS-related adverse event leading to treatment interruption that needed more than 1 week to resolve to grade \leq 1
- graft-versus-host disease
- investigator's decision that a change of therapy (including immediate HSCT) is in the subject's best interest

Females who become pregnant while on study through 4 weeks after receiving the last dose of study drug will not receive subsequent scheduled doses and will be followed for safety until the end of study visit.

Males on study through 4 weeks after receiving the last dose of study drug must practice sexual abstinence or use a condom while on study through 4 weeks after receiving the last dose of study drug.

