### 6.7 Study-specific Analysis Sets

#### **Dose Limiting Toxicity (DLT) Evaluable Analysis Set:**

DLT Evaluable Analysis Set includes all DLT-evaluable subjects defined as all subjects who have received the doses planned for the respective cohort, and completed the DLT window of 28 days for all cohorts unless he/she drops out before completion of the DLT window for reasons other than a DLT; **exception:** if a subject has received the planned doses in cycle 1 and drops out within 1 week of the completion of the DLT period due to progressive disease, that subject will be considered DLT-evaluable and will not be replaced. The DLT window may also be extended to assess events starting within the window in case the DLT definition is time dependent. The analysis of DLT will be restricted to DLT Evaluable Analysis Set.

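### A subject whose cycle 1 target dose is delayed or made up can count as DLT-evaluable with little or no DLT window left after that dose

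*Protocol*

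**What the plan says.** **Window.** Protocol 6.2.1.3: "The DLT window will start on D1 (start of the administration of the first dose) and last for 28 days for all cohorts". SAP Section 5 repeats this.

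**Evaluability.** Under Protocol 6.2.1.3 a subject is evaluable "if the subject has received the doses planned for the respective cohort, and completed the DLT window of 28 days for all cohorts". SAP 6.7 uses the same two conditions. Neither sets a minimum time after the last or the target dose.

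**Delay and make-up.** Protocol 6.2.1.4 counts a postponed dose as an interruption and, for some events, provides for restart at a lower dose. It adds: "In case of a dose reduction, re-escalation to the target dose can be considered for the next infusion". Where possible, target-dose infusions "should sum up to the planned number of infusions. In this case, the cycle would still be DLT-evaluable". No last day is given. An interruption of more than 21 days for an adverse event leads to permanent discontinuation, with exceptions for neutropenia and for events clearly due to the leukemia.

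**Extension.** SAP 6.7, like Protocol 6.2.1.3: "The DLT window may also be extended to assess events starting within the window in case the DLT definition is time dependent". It therefore covers only events that have already begun, not a late dose.

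**Late events.** Protocol 6.2.1.3 lets the DLRT declare an out-of-window event a DLT. The recommendation must be unanimous, and the event must be possibly related and also more frequent or severe than expected, or persistent. Protocol 3.1.2.2 says DLTs arising after the DLT period will be taken into account in the BLRM. Protocol 10.4.2 has the DLRT review data from after the window.

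**The concern.** The window is tied to the first dose, while the dose being tested may come much later. When a planned dose slips, the window does not slip with it, yet 6.2.1.4 keeps the cycle evaluable once the infusion count is reached. The subject then meets both evaluability conditions although a toxicity from the late target dose would mostly fall outside the window. There it no longer becomes a DLT simply by meeting the listed criteria.

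At stake is the count that feeds the BLRM and the expansion pause rule. Cohorts have 2 to 4 subjects, and the MTD can be declared with 6 treated at that dose (Protocol 3.1.2). One subject wrongly scored as DLT-free can matter when the data are near a boundary.

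**Working it through.** **1. The plan's own figures reproduce.** P(at least 1 DLT) = 1 − (1 − p)^n at p = 0.10 and 0.33 gives 19.0%/55.1% (n = 2), 27.1%/69.9% (n = 3) and 34.4%/79.9% (n = 4). These match Protocol 10.2. The rule P(rate > 0.20) > 0.80 under Beta(0.4, 1.6) returns the boundaries 3, 4, 6, 7, 9, 10, 11, 13 of Protocol Table 26 (SAP Table 1). All these figures assume that every DLT is counted.

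**2. Window left after a dose** = max(0, 28 − (scheduled day + delay)):

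| Dose | On time | +3 days | +8 days | +10 days | +21 days |
|---|---|---|---|---|---|
| D8 (last of 4) | 20 | 17 | 12 | 10 | 0 (D29) |
| D19 (last of 6) | 9 | 6 | 1 (D27) | 0 (D29) | 0 (D40) |

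The 3-day column is the logistical dosing window. The 10-day column is the minimum COVID-19 interruption for an asymptomatic subject who is not fully vaccinated (Protocol Table 5). The 21-day column is the discontinuation limit in 6.2.1.4.

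**3. An 8-day hold without a DLT.** Grade 2 CRS that resolves to grade 1 or less within 7 days is not a DLT (6.2.1.3). The next dose also needs 24 hours at that grade (6.2.1.4, Table 7). So 7 + 1 = 8 days. If the D8 infusion is the one held, it moves to D8 + 8 = D16. Keeping the planned gaps of 4 and 7 days (an assumption), the last two infusions fall on D20 and D27, and 28 − 27 = 1 day remains. An added lower-dose infusion would push the last one later.

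**4. What one unclassified DLT can do near a boundary.**
- Expansion rule, Beta(0.4, 1.6), 6 subjects: P(rate > 0.20) is 0.35 at 1/6, 0.71 at 2/6 and 0.91 at 3/6. Missing one of three DLTs removes a pause. Missing one of two changes nothing.
- Escalation, as an illustration only: a one-dose logit-normal prior with median 0.25 and 5% below 0.05 has logit SD (−1.099 + 2.944)/1.645 = 1.12. P(rate > 0.33) is then 0.04 at 0/6, 0.16 at 1/6 and 0.40 at 2/6, against the 0.25 limit. Missing one of two DLTs turns a blocked dose into an allowed one. Missing a single DLT does not. This is not the trial's two-parameter BLRM, and reading the stated 0.25 as a median is an assumption.

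**5. Sensitivity.** Let f be the share of all DLTs in the trial that are counted, so the observed rate is f × the true rate. The documents give no basis for f.

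| f | P(at least 1 DLT), n = 4, true rate 10% / 33% | P(expansion pause), true rate 30%, R/R / MRD+ |
|---|---|---|
| 1 | 34% / 80% | 79% / 86% |
| 0.9 | 31% / 76% | 67% / 74% |
| 0.75 | 27% / 68% | 46% / 52% |
| 0.5 | 19% / 51% | 14% / 15% |

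Only subjects with delayed doses lower f. The bottom rows would need such delays to be common and most of those subjects' DLTs to be missed.

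**The case against.** The strongest reply is that the protocol already looks past day 28. Section 3.1.2.2 brings DLTs after the DLT period into the BLRM, 6.2.1.3 allows reclassification, and 10.4.1 and 10.4.2 put all adverse events and post-window data before the DLRT. A reader might infer that delayed subjects simply enter the model as DLT-free. The documents do not support that: they can, but they need not. The backstops are still weaker than the primary definition. Reclassification needs unanimity and narrower criteria. Section 3.1.2.2 does not say how a late DLT is coded. The SAP repeats the unanimity rule (Section 5) and the DLRT review (7.1), but not the 3.1.2.2 provision.

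Four other inferences go too far:

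- **That these subjects go unobserved.** They are hospitalized for at least 72 hours after restart (6.2.1.4), and adverse events are collected to at least 30 days after dosing (9.2.1.1). Section 6.6 places the raised CRS risk in the first days after the initial dose and after a dose step. The gap is in classification.
- **That they all had toxicity at the dose and were scored clean.** Many events that would hold dosing for 10 to 21 days are already DLTs or force discontinuation, such as CRS that does not resolve in time and most grade 3 or higher non-hematologic toxicity. The concern covers the remainder: shorter CRS holds, excepted events and COVID-19.
- **That make-up doses well past day 28 are authorized.** The 21-day figure is a discontinuation limit, and 6.2.1.4 speaks of infusions within a cycle, nominally about 14 or 28 days. A dose on D29 or later is an inference from the missing cut-off. The D27 case does not depend on it, but it does need the 6-dose schedule, which the DLRT may or may not adopt.
- **That the expansion review ignores prolonged cycles.** It is timed from completion of the first cycle plus 2 weeks (3.1.3), so a longer cycle postpones it. That moves the meeting, but not the definition of the DLTs it counts.

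**Conclusion.** The gap is real and limited. Protocol 6.2.1.3, 6.2.1.4 and SAP 6.7 together allow a subject with a delay that is not a DLT to count as evaluable and DLT-free with little or no window time after the target dose. This arises mainly on the 6-dose schedule (1 day left after an 8-day hold, none after 10) or after long delays on the 4-dose schedule. Short delays on the 4-dose schedule leave 12 to 17 days and are of little concern.

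Any resulting bias in the DLT rate is downward. Its size cannot be computed, because the documents give neither the frequency of such delays nor the onset timing of DLTs. The decision changes in the working are boundary cases, so they do not show that the MTD will be biased. The conclusion rests on there being no re-anchoring rule or make-up cut-off in the text, and on the planned gaps being kept after a hold. It merits correction because the decision it protects is a safety decision that may rest on as few as 6 subjects.

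**What to change.** Reconcile Protocol 3.1.2.2, 6.2.1.3 and 6.2.1.4 with SAP 6.7. This concerns only how subjects are counted, not how they are dosed.

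1. When a planned cycle 1 dose is delayed or made up, keep the subject pending in the BLRM and in the expansion pause rule until followed for a prespecified time after the last planned dose. One option is the time an undelayed subject on that schedule would have (20 days after D8, 9 after D19). Those lengths follow from the schedule, and the sponsor may justify others.
2. Count any event that meets the DLT criteria in that time as a DLT, without a unanimous DLRT recommendation.
3. State in the SAP how DLTs after the DLT period enter the BLRM.

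Optionally, run the BLRM with and without subjects who reached the target only after unplanned lower doses, since Protocol 3.1.1 notes: "Starting with an initial lower dose may improve tolerability of subsequently administered higher doses".

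**Cost.** Wording in both documents, and an occasional wait. With the schedule-matched follow-up, a delay of d days postpones that subject's result by d days: a D8 dose given on D29 needs follow-up to 29 + 20 = D49, which is 21 days past D28. The wait is therefore up to about 3 weeks, and longer only where the 21-day limit does not apply or extra infusions are given.

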6.3 Other Protocol-required Therapies

All other protocol-required and recommended therapies, including corticosteroids, that are commercially available are not provided or reimbursed by Amgen (except if required by local regulation). The investigator will be responsible for obtaining supplies of these therapies.

Oxygen: Oxygen administration as a supportive measure is permitted during study treatment.

Hydroxyurea: Hydroxyurea may be permitted according to standard practice prior to the first cycle of investigational product treatment for subjects with high WBC ($> 15,000$ cells/ μL or 15 cells $\times 10^9/\text{L}$). Administration of hydroxyurea after the start of AMG 427 may be permitted after discussion with the Amgen medical monitor.

Dexamethasone: Premedication with dexamethasone is required for every cycle before infusion of AMG 427 dosing and prior to each dose step of AMG 427 to mitigate the risk of CRS. When dosed, dexamethasone should be administered as a single IV dose (8 mg) within 1 hour of start of infusion.

Methylprednisolone: may also be utilized as per [Table 6](#) to treat CRS, per institutional practice.

Tocilizumab: Tocilizumab will be used to treat cytokine release syndrome (**Actemra[®]** USPI, 2021), as described in [Table 6](#). In addition, use of prophylactic tocilizumab to mitigate CRS will be tested in a cohort of subjects once final MTD has been established, as described in Section [3.1.2](#). For administration of dexamethasone and tocilizumab after occurrence of CRS, follow guidance in Section [6.6](#). Additional details regarding these protocol-required therapies are provided. **Sites are required to have tocilizumab or siltuximab (if tocilizumab not available) on site for potential treatment of CRS (Sylvant[™] USPI, 2015). If tocilizumab is not available, siltuximab (an anti-IL-6 monoclonal antibody) may be used in the management of cytokine release syndrome, following the criteria outlined in [Table 7](#). The recommended dose of siltuximab is 11 mg/kg administered over 1 hour as an intravenous infusion, consistent with the prescribing information for the treatment of multicentric Castleman's disease (Sylvant[™] USPI, 2015), and the CARTOX Working Group Guidelines for CRS management (Neelapu et al, 2018). Siltuximab may be repeated if needed, in the event that CRS recurs after a subsequent infusion of AMG 427. Siltuximab may not be repeated in an individual subject that develops anaphylaxis to siltuximab, or gastrointestinal perforation after**

siltuximab. A subgroup analysis for those treated with siltuximab will be evaluated, including CRS outcomes, safety, and PK data.

Anakinra: The interleukin-1 receptor (IL-1R) blocker/inhibitor will be used for symptoms of CRS-related ICANS as per [Table 8](#). In preclinical models, Anakinra has shown to abolish both CRS and neurotoxicity, resulting in substantially extended leukemia-free survival (Norelli et al, 2018). Interleukin-1 receptor inhibitor has been found to be useful in managing CRS related acute respiratory distress syndrome and ICANS/neurotoxicity (Morris et al, 2021).

(CLOSED) Etanercept: Etanercept will be used prophylactically to mitigate signs/symptoms/severity of cytokine release syndrome. [REDACTED]

6.4 Hepatotoxicity Stopping and Rechallenge Rules

Subjects with abnormal hepatic laboratory values (eg, alkaline phosphatase [ALP], AST, ALT, total bilirubin [TBIL]) or international normalized ratio [INR]) or signs/symptoms of hepatitis may meet the criteria for withholding of investigational product. Withholding is either permanent or conditional depending upon the clinical circumstances discussed below (as specified in the FDA Guidance for Industry Drug-Induced Liver Injury: Premarketing Clinical Evaluation, July 2009).

